ANC	absolute neutrophil count
APC	antigen presenting cells
AST	aspartate aminotransferase
ATG	antithymocyte globulin
ATS	American Thoracic Society
AUC _{0-t}	area under the plasma or serum concentration-time curve from time = 0 to the last measurable concentration at time = t
[REDACTED]	[REDACTED]
BID	twice daily
BOS	bronchiolitis obliterans syndrome
cGVHD	chronic graft-versus-host disease
CI	confidence interval
CLAD	chronic lung allograft dysfunction
Cl/F	apparent oral dose clearance
C _{max}	maximum observed concentration
C _{min}	minimum observed plasma or serum concentration over the dose interval
CMV	cytomegalovirus
CNI	calcineurin inhibitor
COVID-19	coronavirus disease 2019
CsA	cyclosporine a
CTCAE	Common Terminology Criteria for Adverse Events
CYP	cytochrome P450
DNA	deoxyribonucleic acid
ECG	electrocardiogram
eCRF	electronic case report form
EOT	end of treatment
EQ-5D-3L	EuroQol EQ-5D 3 level version
ERS	European Respiratory Society
FAS	full analysis set
FDA	Food and Drug Administration

Abbreviations and Special Terms	Definition
FEF ₂₅₋₇₅	forced expiratory flow at 25–75% of forced vital capacity
FEV ₁	forced expiratory volume in 1 second
GVHD	graft-versus-host disease
HBV	hepatitis B virus
HCV	hepatitis C virus
HIV	human immunodeficiency virus
HSCT	hematopoietic stem cell transplant
ICF	informed consent form
ICH	International Council on Harmonisation of Technical Requirements for Registration of Pharmaceuticals for Human Use
IEC	independent ethics committee
IRB	institutional review board
IRT	interactive response technology
ISHLT	International Society for Heart and Lung Transplantation
JAK	Janus kinase
MedDRA	Medical Dictionary for Regulatory Activities
mTORi	mTOR inhibitor
ORR	overall response rate
PCR	polymerase chain reaction
PD	pharmacodynamic
PK	pharmacokinetic
QD	once daily
RAS	restrictive allograft syndrome
RNA	ribonucleic acid
RP2D	recommended Phase 2 dose
SAE	serious adverse event
SARS-CoV-2	severe acute respiratory syndrome coronavirus 2
SGRQ	St Georges Respiratory Questionnaire
SoA	schedule of activities
TB	tuberculosis
TEAE	treatment-emergent adverse event
ULN	upper limit of normal

1. PROTOCOL SUMMARY

Protocol Title: An Open-Label, Single-Arm, Phase 1/2 Study Evaluating the Safety and Efficacy of Itacitinib in Participants With Bronchiolitis Obliterans Syndrome Following Lung Transplantation

Protocol Number: INCB 39110-214

Objectives and Endpoints:

[Table 1](#) presents the primary and key secondary objectives and endpoints of the study.

[figure not shown]
Table 1: Primary and Key Secondary Objectives and Endpoints

Objectives	Endpoints
Primary	
Phase 1	
To identify an appropriate dose of itacitinib as a treatment for Grade 1 through 3 BOS following lung transplantation.	Frequency, severity, and duration of AEs; assessment of changes in safety and FEV ₁ ; and assessment of changes in laboratory parameters, PK, and PD.
Phase 2	
To evaluate the efficacy of itacitinib as a treatment for Grade 1 through 3 BOS following lung transplantation.	FEV ₁ response rate from baseline through the Week 12 visit, defined as the proportion of participants demonstrating a $\geq 10\%$ absolute increase in FEV ₁ compared to baseline.
Key Secondary	
Phase 1 and Phase 2	
To evaluate duration of FEV ₁ response in participants with Grade 1 through 3 BOS following lung transplantation who are treated with itacitinib.	Duration of FEV ₁ response, defined as the time of the onset of response ($\geq 10\%$ absolute increase in FEV ₁ compared to baseline) to BOS progression or loss of clinical benefit as determined by the investigator.
To evaluate time to progression in participants with Grade 1 through 3 BOS following lung transplantation who are treated with itacitinib.	Time to progression, defined as the interval between the start of treatment and BOS progression ($\geq 10\%$ absolute decrease in FEV ₁ compared to baseline), or death.
To evaluate quality of life outcomes in participants with Grade 1 through 3 BOS following lung transplantation who are treated with itacitinib.	
Change from baseline in SGRQ total score.Change from baseline in QOL-SF-12 questionnaire.Categorical summary or change from baseline in EQ-5D-3L questionnaire.

Overall Design:

Study Phase	Phase 1/2
Clinical Indication	Post-lung transplant BOS
Population	Males and females who are at least 18 years of age who have undergone double lung transplantation at least 1 year before screening and have a diagnosis of Grade 1 through 3 BOS.
Number of Participants	Phase 1: Approximately 24 participants, to be treated at 3 different dose levels (n = 8 each) Phase 2: Up to approximately 55 participants
Study Design	Phase 1: Randomized, open-label Phase 2: Single-arm, open-label
Estimated Duration of Study	Up to 30 days for screening, continuous treatment as long as participants are receiving benefit and have not met any criteria for treatment discontinuation, 30 days for safety follow-up, and participants enrolled in Phase 2 will be followed for long-term survival and retransplantation status. Study participation, including survival follow-up, is expected to average approximately 24 months per participant.
Study Steering Committee	A steering committee comprised of the coordinating PI and select sponsor personnel will review the cumulative Phase 1 data and provide a recommendation for the Phase 2 dose.

Figure 1: Study Design Schema

^a Not inclusive; see Section 4 for complete eligibility criteria.

Adherence to the study design requirements, including those specified in the SoA (see [Table 2](#)), is essential and required for study conduct.

Table 2: Schedule of Activities

Visit Day (Range)	Screening	Treatment							EOT	Safety Follow-Up (30 d + 7 d)	Notes
	Days -30 to -1	Baseline (Day 1)	Week 1 (± 1 d)	Week 2 (± 3 d)	Weeks 4 and 8 (± 7 d)	Week 12 (± 7 d)	Week 16 and Q4W thereafter (± 14 d)				
Administrative procedures											
Informed consent	X										See Section 8.1.1 for details.
Register visit in IRT	X	X			X	X	X	X			See Section 8.1.3 for details.
Inclusion/exclusion criteria	X	X									See Section 5 for details.
Demography	X										See Section 8.1.5 for details.
Relevant medical and transplant history	X										See Sections 8.1.5 and 8.1.6 for details.
Prior/concomitant medications	X	X	X	X	X	X	X	X			See Section 6.3 for details.
Study drug dispensing and accountability		X			X	X	X	X			See Section 6.4 for details.
Dispense reminder card		X	X	X	X	X	X	X			See Section 8.1.4 for details.
Safety assessments											
AE assessment	X	X	X	X	X	X	X	X			See Section 8.3.1 for details.
Comprehensive physical	X										See Section 8.3.2 for details.
Targeted physical exam		X	X	X	X	X	X	X			See Section 8.3.2 for details.
Vital signs/weight	X*	X	X	X	X*	X*	X*	X*	X		See Section 8.3.3 for details. * Weight performed.
12-Lead ECG	X	As clinically indicated						X			See Section 8.3.4 for details.
Disease assessments											
Spirometry (FEV ₁ and FVC)	X	X	X	X	X	X	X	X			See Section 8.2.1 for details.

Table 3: Schedule of Laboratory Assessments

Procedure	Screening		Treatment					EOT	Safety Follow-Up (30 d ± 7 d)	Notes	
	Day -30 to -1	Baseline (Day 1)	Weeks 1 and 2 (± 3 d)	Week 4 (± 7 d)	Week 8 (± 7 d)	Week 12 (± 7 d)	Week 16 and Q4W thereafter (± 14 d)				
Laboratory safety assessments											
Hematology	X	X*	X	X	X	X	X	X	X	* May be omitted at baseline if screening hematology within 14 days.	
Blood chemistry	X	X*	X	X	X	X	X	X	X	* May be omitted at baseline if screening chemistry within 14 days.	
Lipid panel	X					X*	X*	X*	X*	* Every 12 weeks starting at Week 12 (eg, Week 24, 36).	
Coagulation	X	X*	X	X	X	X	X	X		* May be omitted at baseline if screening coagulation within 14 days.	
Hepatitis screening	X										
CNI and mTORi (as applicable) levels	X	X	X	X	X					Tacrolimus/CsA and mTORi levels (as applicable) to be monitored from screening through Week 8.	
CMV PCR		X	X	X	X	X	X	X		See Section 8.3.5 for details.	
Serum pregnancy test	X							X		Women of childbearing potential only.	
Urine pregnancy test				X	X	X	X			Women of childbearing potential only.	

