2.3. Benefit/Risk Assessment

The potential benefit for itacitinib in post-lung transplant BOS patients is derived from the biologic similarity to cGVHD, with each entity sharing common features such as increased proinflammatory cytokines, presence of CD4, CD8, and Th17 cell infiltrate, as well as subsequent recruitment of B cell, NK cell, and APCs. Preclinical models and small clinical studies have demonstrated significant activity when JAK inhibitors are used in cGVHD, including improvement and stabilization in FEV₁ in patients with lung cGVHD, suggesting that JAK inhibitors may also have potential utility in treating post-lung transplant BOS.

Risks to study participants may be minimized by compliance with the eligibility criteria and study procedures as well as close clinical monitoring and adherence to dose modification guidelines for toxicity. Additionally, the safety profile of the 3 doses to be evaluated has been established in prior studies. Risks related to myelosuppression and bleeding should be further managed in accordance to standard institutional practices for administration of hematopoietic growth factors and transfusion support. Risks related to infections should be managed through continued prophylaxis and prompt identification and treatment.

In September 2021, analysis of the data from the Phase 1 portion of the study revealed evidence of clinical benefit in a subset of participants with a manageable safety profile. The sponsor decided not to proceed to Phase 2 of the study for reasons unrelated to the benefit/risk of itacitinib in the study population. The sponsor will continue to consider the benefit/risk favorable for participants who are continuing on itacitinib as of Protocol Amendment 5.

There may be unforeseen and potentially serious risks with itacitinib. More detailed information about the known and expected benefits and risks and reasonably expected AEs of itacitinib may be found in the [IB](#).

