10.4.2. Efficacy Analysis

Secondary efficacy analysis will be conducted for the full analysis data set as follows:

- Duration of FEV₁ response is defined as the time of the onset of response ($\geq 10\%$ absolute increase in FEV₁ compared to baseline) to BOS progression or loss of clinical benefit. It will be estimated by the Kaplan-Meier method.
- Summary statistics will be provided for change from baseline in SGRQ total score at each scheduled visit.
- Summary statistics will be provided for change from baseline in the QOL-SF-12 questionnaire at each scheduled visit.
- Summary statistics will be provided for the EQ-5D-3L questionnaire at each scheduled visit.
- Time to progression, defined as the interval between the start of treatment and BOS progression, defined as a $\geq 10\%$ absolute decrease in FEV₁ from pretreatment baseline, observed in at least 2 consecutive spirometric assessments at least 3 weeks apart, or death. It will be estimated by the Kaplan-Meier method.
- Overall survival, defined as the time from the date of start of study drug to the date of retransplantation or death due to any cause. The Kaplan-Meier method will be used. Summary statistics will be provided.

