### 2.2. Study Objectives and Endpoints

Table 1 presents the objectives and endpoints.

**Table 1:** Objectives and Endpoints

Objectives	Endpoints
Primary	
Phase 1	
To identify an appropriate dose of itacitinib as a treatment for Grade 1 through 3 BOS following lung transplantation.	Frequency, severity, and duration of AEs; assessment of changes in safety and FEV 1 ; and assessment of changes in laboratory parameters, PK, and pharmacodynamics.
Phase 2	
To evaluate the efficacy of itacitinib as a treatment for Grade 1 through 3 BOS following lung transplantation.	FEV 1 response rate from baseline through the Week 12 visit, defined as the proportion of participants demonstrating a $\geq$ 10% absolute increase in FEV 1 compared to baseline.
Secondary	
Phase 1 and Phase 2	
To evaluate duration of FEV 1 response in participants with Grade 1 through 3 BOS following lung transplantation who are treated with itacitinib.	Duration of FEV 1 response, defined as the time of the onset of response ( $\geq 10\%$ absolute increase in FEV 1 compared to baseline) to BOS progression ( $\geq 10\%$ absolute decrease in FEV 1 compared to baseline) or loss of clinical benefit as determined by the investigator.
To evaluate time to progression in participants with Grade 1 through 3 BOS following lung transplantation who are treated with itacitinib.	Time to progression, defined as the interval between the start of treatment and BOS progression (≥ 10% absolute decrease in FEV₁ compared to baseline), or death.
To evaluate quality of life outcomes in participants with Grade 1 through 3 BOS following lung transplantation who are treated with itacitinib.	
 
Change from baseline in SGRQ total score.
 
Change from baseline in QOL-SF-12 questionnaire.
 
Categorical summary or change from baseline in EQ-5D-3L questionnaire.
 

To evaluate the PK of itacitinib in the study population.	C max , C min , t max , AUC 0-t , and Cl/F.

**Table 1:** Objectives and Endpoints (Continued)

Objectives	Endpoints
Secondary (continued)	
Phase 2 only	

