### 7.1. General Considerations

All efficacy analyses will be done by treatment group using the FAS. The SGRQ Total Score, QOL-SF-12 Questionnaire, and EQ-5D-3L analyses will not be performed due to the early study termination.

For continuous measurements, summary statistics will include sample size, mean, median, standard deviation, standard error of the mean, minimum, and maximum. For all continuous variables, both the actual value and change and/or percentage from baseline (if available) will be analyzed. For categorical measurements, summary statistics will include sample size, frequency, and percentages.

All by-visit analyses will include the EOT and follow-up visits if the data are available.

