#### 7.4.3. SGRQ Total Score

The SGRQ (Jones et al 1991) is a disease-specific instrument designed to measure impact on overall health, daily life, and perceived well-being in patients with obstructive airway disease. It consists of 50 items covering 3 domains: symptoms (8 items), activity (16 items), and impacts (26 items).

A component score will be calculated for each of the 3 domains. If more than 2 items in the symptoms domain are missing, the symptom component score will set to be missing. If more than 4 items in the activity domain are missing, the activity component score will set to be missing. If more than 6 items in the impacts domain are missing, the impacts component score will set to be missing.

One total score will be calculated if none of the component scores is missing. All scales have a score range between 0 and 100 with higher scores indicating a worse quality of life.

Summary statistics will be provided for change from baseline in SGRQ component scores and the total score at each scheduled visit.

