### 11.1. Changes to Protocol-Defined Analyses

Not applicable.

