## 11.2. Changes to the Statistical Analysis Plan

#### **11.2.1. Amendment 1**

The following updates were made for SAP Amendment 1 to align with early study termination:

- The planned tables, figures, and listings were updated in Appendix A to remove those that were not needed.
- Analyses for SGRQ Total Score, QOL-SF-12 Questionnaire, and EQ-5D-3L were removed.
- Text was updated to address the analyses not being performed.

Other minor administrative changes have been incorporated throughout and are noted in the redline version of the document.

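### Phase 1 quality-of-life data from visits before Protocol Amendment 5 are dropped for early termination, which explains only the later visits, so a stated objective goes unanswered

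*Protocol*

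**What the plan says.** **The objective.** Protocol Table 1 lists quality of life among the key secondary objectives: "To evaluate quality of life outcomes in participants with Grade 1 through 3 BOS following lung transplantation who are treated with itacitinib". Its endpoints are SGRQ total score, SF-12 and EQ-5D-3L. Protocol Table 6 and SAP Table 1 repeat it as a secondary objective. In SAP Table 1 it sits under the subheading "Phase 1 and Phase 2".

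**The planned analysis.** Protocol 10.4.2 still reads, for the first instrument, "Summary statistics will be provided for change from baseline in SGRQ total score at each scheduled visit", with matching lines for the other two. SAP 7.4.3 says "Summary statistics will be provided for change from baseline in SGRQ component scores and the total score at each scheduled visit", and 7.4.4 and 7.4.5 do the same for SF-12 and EQ-5D-3L.

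**The cancellation.** SAP 7.1 says "The SGRQ Total Score, QOL-SF-12 Questionnaire, and EQ-5D-3L analyses will not be performed due to the early study termination". SAP 11.2.1 logs it: "Analyses for SGRQ Total Score, QOL-SF-12 Questionnaire, and EQ-5D-3L were removed". Appendix A contains neither a table nor a listing for any questionnaire. SAP 11.1, on changes to protocol-defined analyses, reads "Not applicable".

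**The termination.** Protocol 2.3 reports a September 2021 analysis of Phase 1 data and then says "The sponsor decided not to proceed to Phase 2 of the study for reasons unrelated to the benefit/risk of itacitinib in the study population". The Amendment 5 summary (30 NOV 2021) says that assessments were updated or removed for ongoing participants because the study would not be completed, and names the patient-reported outcomes section among those affected. The current protocol has no such section and no questionnaire row in its schedules. Spirometry remains at every treatment visit and at EOT.

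**The concern.** What stopped was enrolment and the move to Phase 2. The objective also belongs to Phase 1, and questionnaires were protocol assessments until Amendment 5. A reason that took effect in late 2021 is being used to set aside data that would have been collected before then.

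Two things are at stake. First, an objective that both documents still state will have no answer in the report, not even a listing. Second, these are the only patient-reported endpoints among the key secondary ones. Omitting them from an open-label study without a reason based on the data invites a question about selective non-reporting, and a short descriptive table would remove it.

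The SAP also gives a programmer conflicting instructions: 7.1 says the analyses will not be done, while 7.4.3 to 7.4.5 say the summaries will be provided.

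**Working it through.** The plan gives no sample size, SD or precision for quality of life, so there is no stated figure to reproduce. The check is mainly a comparison of passages.

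**1. How much of the objective set is affected (Protocol Table 1).** There are three key secondary objectives: duration of FEV1 response, time to progression, and quality of life. They carry 1 + 1 + 3 = 5 endpoints. Quality of life is 1 of 3 objectives and 3 of 5 endpoints.

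**2. What output each objective keeps (SAP Appendix A).**
- Duration of FEV1 response: Table 2.3.1 and Listing 2.6.4.
- Time to progression or death: Table 2.3.2 and Listing 2.6.3.
- Quality of life: none.

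Laboratory values, vital signs and ECGs also have no summary table, but they keep listings (2.8.1 to 2.8.4, 2.9.1, 2.10.1).

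**3. Which visits the stated reason covers.**
- After Amendment 5: questionnaires stopped because of the termination. The reason fits.
- Before Amendment 5: questionnaires were in the protocol. SAP 7.4.5 has EQ-5D-3L starting on Day 1, and SAP 7.4.3 and 7.4.4 define change from baseline at each scheduled visit for SGRQ and SF-12. The reason does not fit.

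**4. Dates.** The decision not to open Phase 2 is not dated exactly, but it was made no later than 30 NOV 2021. From that date:
- to the original SAP (12 APR 2023): 498 days;
- from the original SAP to SAP Amendment 1 (26 AUG 2024): 502 days;
- total: 498 + 502 = 1,000 days, about 33 months.

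The termination was therefore already known when the original SAP was written.

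**5. Precision if the data were summarised.** The 95% CI half-width for a mean change is t(0.975, n − 1) × SD / √n. Inputs are the planned Phase 1 numbers (Protocol 10.1.1: 24 in total, 8 per dose level) and complete data, which is an assumption.
- Pooled, n = 24: 2.069 / 4.899 = 0.42 SD.
- Per dose level, n = 8: 2.365 / 2.828 = 0.84 SD.

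The documents give no SD for SGRQ change. For an assumed SD of 10 to 20 points, the half-width is 4.2 to 8.4 points pooled and 8.4 to 16.7 points per dose level.

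**The case against.** The case for the sponsor has real substance.

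- **Termination did reach Phase 1.** The participants still on treatment were Phase 1 participants, and Amendment 5 cut their questionnaires. A reader might infer that the reason has no bearing on Phase 1 at all. The documents contradict that for later visits.
- **FEV1 is not in the same position.** A reader might infer that the reason applies equally to the retained endpoints. It does not: spirometry continued after Amendment 5, the retained time-to-event endpoints depend on that later follow-up, and FEV1 is part of the Phase 1 primary endpoint.
- **The cuts are broad and open.** SAP Amendment 1 trimmed many displays, and Appendix A also lacks summary tables for laboratory values, vital signs, ECGs, and transplant and BOS history. The questionnaire removal is stated in both 7.1 and 11.2.1. A reader might infer that an inconvenient outcome was hidden. Nothing in the documents supports that, and the late date of the removal is not evidence of it.
- **The data are inferred.** The documents do not give the number enrolled, questionnaire completion, or the SGRQ and SF-12 visit schedule. Only EQ-5D-3L has an explicit Day 1 start.
- **The endpoints are descriptive and the numbers small.** No hypotheses are tested, and precision by dose level is poor.

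All of this limits the point. None of it explains dropping visits before Amendment 5. If the data were too incomplete to summarise, the SAP could say so, and it does not. Small numbers are not a reason either, because every efficacy analysis here is descriptive and duration of response, which is kept, rests on responders alone.

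**Conclusion.** The concern holds in a limited form. Early termination accounts for missing questionnaires after 30 NOV 2021. It does not account for setting aside Phase 1 questionnaires from earlier visits. Followed as written, the SAP leaves one stated secondary objective with no output, while Protocol 10.4.2 and SAP 7.4.3 to 7.4.5 still promise it.

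This is an inadequate justification and an unanswered objective. It is not concealment, and it does not affect the Phase 1 dose-selection objective or the FEV1 analyses. It is a cheap improvement worth making.

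The conclusion assumes that questionnaires were completed at some visits before Amendment 5. That is a strong inference from their being protocol assessments until then, but the documents do not confirm it. The precision figures further assume the planned 24 participants and complete data; real intervals would be wider if either falls short.

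**What to change.** 1. In SAP 7.1, replace the cancelling sentence with a statement that questionnaire data collected before Protocol Amendment 5 took effect will be summarised descriptively as set out in 7.4.3 to 7.4.5, by dose level and pooled, with the number completing at each visit. The pooled column adds to the by-treatment-group rule in 7.1 and should be named there.
2. Restore one summary table per instrument and a listing to Appendix A, and update the 11.2.1 entry to match.
3. If the data prove too sparse to summarise, provide the listing and the completion counts, give sparseness as the reason in 7.1, mark 7.4.3 to 7.4.5 as not performed, and record the change in SAP 11.1, which now reads "Not applicable".

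**Cost.** Three tables and a listing whose methods are already written, with no new data collection. The results will be imprecise, especially by dose level, and should be labelled descriptive.
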